### Document Version History

Version Number	Reason for Update	Updated By:	Date
0.01	Creation of new SAP	[name]	24 Apr 2014
0.02	Updates to SAP	[name]	16 Oct 2014
0.03	Writing Group discussion	[name]	30 Oct 2014
0.04	Trial Steering Group discussion	[name]	12 Nov 2014
0.05	Confirmation of discussions	[name]	04 Feb 2015
0.06	Final discussions	[name]	19 Mar 2015
1.0	Final signed version	[name]	21 May 2015

#### 2 List of Abbreviations

.

6-MP	6-Mercaptopurine
CI	confidence interval
CONSORT	CONsolidated Standards of Reporting Trials
DMC	Data monitoring committee
ECTU	Edinburgh Clinical Trials Unit
EQ-5D	EuroQol 5 dimensions health outcome questionnaire
IBDQ	Inflammatory bowel disease questionnaire
IQR	Inter quartile range
ITT	Intention-to-treat
Max	Maximum
Min	Minimum
n	Number of patients with an observation
SAP	Statistical Analysis Plan
SD	Standard Deviation
SF-36	Short form health survey – 36 questions
TGN	Thioguanine
TOPPIC	Trial acronym for 'Randomised Controlled Trial of 6-
	Mercaptopurine Versus Placebo to Prevent Recurrence of Crohn's
	Disease Following Surgical Resection'
TPMT	Thiopurine s-methyltransferase

#### 3 Introduction

This document details the criteria to be used for the definition of the analysis populations and the statistical methodology for analysis for the TOPPIC trial, a randomised trial of 6-mercaptopurine versus placebo to prevent recurrence of Crohn's disease following surgical resection. This document has been compiled according to the Edinburgh Clinical Trials Unit (ECTU) standard operating procedure (SOP) "Statistical Analysis Plans" and has been written based on information contained in the study protocol version 13, dated 29 April 2015.

TOPPIC is a multicentre, randomised, parallel-group, placebo-controlled trial. Treatment allocation is a 1:1 ratio. Patients are randomised to either 6-mercaptopurine or matched placebo control. The aim was to recruit 234 patients.

#### 4 Statistical Methods Section from the Protocol

The primary outcome variable is postoperative recurrence of Crohn's Disease and it's timing if it recurs. Analysis will be by intention-to-treat and will be based on the application of Cox proportional hazards model. The primary analysis will include terms for the treatment, the variables on which the randomisation was stratified and adjusted for baseline values of previous treatment with 6MP and previous treatment with Azathioprine.

The quality of life variables will be analysed using a repeated measures analysis of covariance to evaluate treatment and treatment by time interactions.

The use of faecal calprotectin as a non-invasive marker of disease recurrence will be examined in two ways. It will be firstly considered as a time dependent covariate in the Cox proportional hazards model described above. Secondly, levels will be compared descriptively between those with negative or positive colonoscopies at 12 and 36 months. Similarly, 6MP drug metabolite levels will be also considered as a time dependent covariate in the Cox proportional hazards model.

Exploratory analyses will investigate the inclusion of the clinical, genetic and serological markers in the model. The models will be used to develop a simple scoring system to predict the risk of recurrence. The sample size will be too small to use a split sample approach to validate the prediction, but the use of a simple scoring system will mitigate to some degree the more extreme effects of using observed regression coefficients to define the risk. During the period after trial recruitment, data from new patients will provide limited short-term validation of the predictions.

#### 5 Overall statistical principles

Health economic analyses will not form part of the statistical report.

All analyses will be intention to treat (ITT), except analyses of safety reporting, where patients will be analysed according to the treatment they received. The ITT population will include all patients who have been randomised into the TOPPIC study. Patients will be analysed in the group to which they were randomised, regardless of treatment received. For analysis according to treatment received, patients will be in the 6-MP group if they receive any 6-MP tablets, and the placebo group if they did not receive any 6-MP tablets.

In general terms, categorical data will be presented using counts and percentages, whilst continuous variables will be presented using the mean, median, standard deviation (SD), minimum, maximum, inter quartile range (IQR) and number of patients with an observation (n), using the format presented in the examples 1 and 2 below. Data will be split by timepoint where applicable.

Parameter	Timepoint / visit	Statistic/ category	6-MP	Placebo	Overall
			N=xx	N=xx	N=xx
Parameter A	Timepoint x	Category 1	xx (%)	xx (%)	xx (%)
		Category n	xx (%)	xx (%)	xx (%)

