#### 6 List of analyses

#### 6.1 Recruitment and retention

The date of first and last patient randomised, the number of patients randomised, and the number of centres that recruited patients, will be reported.

A CONSORT flow chart will be provided by the TOPPIC Trial Manager. This will show the number and percentage of patients considered for randomisation, randomised, dosed, completed and discontinued by treatment and overall. Reasons for noninclusion in the study (prior to randomisation) will be categorised, as in the data monitoring committee (DMC) reports. The number of patients discontinued early from the study will be summarised by reason for withdrawal and treatment.

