#### 6.3 Adherence with trial protocol and allocated treatment

No formal statistical testing will be performed. The following will be presented:

- Number and percentage of patients who were ineligible for inclusion in trial (if any it should not have been possible to randomise such patients).
- Numbers of patients who were randomised but never treated.
- Numbers of patients who took trial medication for the full 3 years, and those who stopped early.

For those who stopped early, they will be categorised as:

Primary outcome-related event Other adverse event Blood test result Other reasons

Time to stopping medication will be presented as a Kaplan-Meier plot, split by allocated treatment.

 Prescribed dose will be summarised. Dose at final visit compared with dose at first visit will be summarised as:

> Dose increased Dose stayed the same Dose decreased Trial medication stopped early

- A summary of patients attending and withdrawing at each visit will be presented, together with reasons for withdrawal.
- A listing of patients where the blind was broken early will be presented, including details of allocation, timing and reason for breaking blind, and outcome.

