#### 6.7 Safety analyses

- 1. Adverse Events (AEs) will be summarised by treatment and by severity, causality and seriousness. No formal statistical analysis will be performed. A listing will be produced detailing each event, and what happened to the patient subsequently.
- 2. Details will be provided of any patients who become pregnant or who have a partner who becomes pregnant during the study. A listing will be produced detailing each event, and what happened to the pregnancies subsequently.
- Blood safety monitoring tests of interest will be summarised by treatment and visit. Abnormal laboratory results outside of the normal reference range will also be summarised. Results of particular interest are: ALT, Alk Phos, Albumin, CRP, WBC, haemoglobin, neutrophils and lymphocytes.

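### The as-treated safety rule makes placebo a residual class, so patients who received no tablets, including those randomised to 6-MP, count as placebo-treated

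*SAP*

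**What the plan says.** SAP Section 5 makes intention to treat the general rule, "except analyses of safety reporting, where patients will be analysed according to the treatment they received". It then gives a two-way assignment: "patients will be in the 6-MP group if they receive any 6-MP tablets", "and the placebo group if they did not receive any 6-MP tablets". There is no third category for patients who received neither product.

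The only population defined by membership is the intention-to-treat one: "The ITT population will include all patients who have been randomised into the TOPPIC study". No safety set conditional on a dose is defined.

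Two other sections allow for patients who are randomised but not dosed. Section 6.1 has the CONSORT chart show patients "randomised, dosed, completed and discontinued by treatment and overall", and Section 6.3 lists "Numbers of patients who were randomised but never treated" as an item to report. Section 6.7 says "Adverse Events (AEs) will be summarised by treatment and by severity, causality and seriousness" and does not exclude undosed patients.

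**The concern.** The rule does not carry out the principle stated just before it. A patient randomised to 6-MP who received no tablets appears under placebo, which is neither the allocated treatment nor the treatment received. A patient randomised to placebo who received no tablets keeps the right arm label but is still counted as exposed to placebo.

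The effect is one-sided. Untreated patients from both arms sit in the placebo denominator and none sit in the 6-MP denominator. If untreated patients have fewer recorded adverse events than treated placebo patients, the placebo percentage falls and 6-MP looks relatively more toxic. The descriptive tables are the only comparison of safety that the SAP plans, so a reader has no separate analysis against which to check them.

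**Working it through.** The SAP states no figure on this point, so there is none to reproduce. The check applies the rule case by case and then illustrates its size.

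**Step 1: classification under the Section 5 wording**

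| Randomised to | Received | Safety group under the rule | Matches treatment received? |
|---|---|---|---|
| 6-MP | 6-MP | 6-MP | Yes |
| 6-MP | nothing | placebo | No; also leaves the allocated arm |
| placebo | placebo | placebo | Yes |
| placebo | nothing | placebo | No; arm label unchanged |

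**Step 2: inputs**

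- From SAP Section 3: 234 patients planned at 1:1, so 234/2 = 117 per arm.
- Assumed, because the SAP gives no values: k6 and kP, the never-treated patients randomised to 6-MP and to placebo; p, the adverse-event risk in treated patients, taken as equal in both arms so that the correct difference is zero; q, the recorded adverse-event rate in never-treated patients.

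**Step 3: formulas**

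- 6-MP denominator = 117 − k6; 6-MP rate = p.
- Placebo denominator = (117 − kP) + kP + k6 = 117 + k6.
- Placebo rate = [(117 − kP)·p + (kP + k6)·q] / (117 + k6).
- Artefactual gap = p − placebo rate = (k6 + kP)·(p − q) / (117 + k6).

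**Step 4: results with 5 never treated in each arm**

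The groups become 112 (6-MP) and 122 (placebo), so the gap is (10/122)·(p − q) = 0.082·(p − q).

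| p | Placebo rate, q = 0 | Gap, q = 0 | Gap, q = p/2 | Gap, q = p |
|---|---|---|---|---|
| 10% | 11.2/122 = 9.2% | 0.8 points | 0.4 | 0 |
| 30% | 33.6/122 = 27.5% | 2.5 points | 1.2 | 0 |
| 60% | 67.2/122 = 55.1% | 4.9 points | 2.5 | 0 |

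**Step 5: sensitivity to the number never treated (q = 0, p = 60%)**

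- 2 per arm: (4/119) × 60 = 2.0 points (placebo rate 58.0%).
- 12 per arm: (24/129) × 60 = 11.2 points (placebo rate 48.8%). This supposes that 12/117, about 10% of each arm, received nothing.
- None: zero.

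The sign depends on p − q. If untreated patients had more recorded events than treated placebo patients, the gap would reverse.

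**Step 6: under a dose-based definition**

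The placebo denominator would be 117 − kP and the placebo rate p, whatever k6 and kP are.

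**The case against.** The strongest reply is that the harm is not shown. Section 6.3 lists never-treated patients as something to report, and the number may be zero. Section 6.7 does not confine adverse events to time on treatment, so an untreated patient may still have events recorded after surgery. Some may even go untreated because of an early complication, which could reverse the direction. Any distortion would also be visible, because dosed and never-treated numbers are reported and each adverse event is listed. All of this stands. It makes the dilution conditional and lowers the severity, but it does not make the assignment rule right.

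A second reply concerns wording. Section 5 speaks of receiving tablets, not of taking them. If that means dispensed, a 6-MP patient who was given tablets and took none stays in the 6-MP group, and only patients never dispensed anything are affected. This also stands, and it is a reason to define the word.

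A reader might draw four stronger conclusions that the SAP does not support:

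- **Laboratory abnormality percentages are diluted in the same way.** Section 5 leaves missing observations out of percentages. An untreated patient without blood results drops out, and one with results contributes a real value. Laboratory tables are affected only in the second case.
- **Untreated patients from both arms change group.** Only those randomised to 6-MP do.
- **The rule might count 6-MP from outside the trial.** In context, treatment received means the two randomised treatments, so this reading is strained.
- **An inferential result is at risk.** Section 6.7 says "Adverse Events (AEs) will be summarised by treatment and by severity, causality and seriousness. No formal statistical analysis will be performed", and the efficacy analyses are by intention to treat.

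**Conclusion.** The rule is wrong as written. It defines the placebo safety group by the absence of 6-MP, contradicts the treatment-received principle in the same paragraph, and is not corrected elsewhere in the SAP. This is not detail that a SAP may leave to the protocol, since Section 3 gives this document the task of defining the analysis populations and Section 5 states the rule in full.

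The misclassification follows from the wording alone. The bias does not: it needs at least one never-treated patient and a lower recorded event rate in such patients, and the SAP gives neither. The illustrated gaps of 0.8 to 4.9 points rest on 5 never treated per arm, no events among them, and equal true risks of 10% to 60%. They show what the rule can do and do not predict what it will do; the effect may be small or nil. No test or type I error is involved. Severity is moderate to minor.

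**What to change.** Amend Section 5, with a cross-reference in Section 6.7, to state that:

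- the as-treated safety population is all randomised patients who received at least one dose of trial medication;
- patients are in the 6-MP group if they received any 6-MP trial tablet, and in the placebo group if they received placebo tablets only;
- receiving means either dispensed or taken, with one chosen and used throughout;
- never-treated patients and any events they have are listed separately by allocated arm.

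This costs a few sentences. The dosed and never-treated counts are already planned under Sections 6.1 and 6.3, so no new data should be needed if receiving is defined by what the trial already records. The change should be made before the safety tables are produced.

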#### Example 1. Data presentation for categorical data

#### Example 2.Data presentation for continuous data

Parameter	Timepoint / visit	Statistic/ category	6-MP	Placebo	Overall
			N=xx	N=xx	N=xx
Parameter	Timepoint x	Mean	XX	XX	xx
		Median	xx	xx	xx
		SD	xx	xx	xx
		Q1, Q3	xx, xx	xx, xx	xx, xx
		Min, Max	xx, xx	XX, XX	xx, xx
		n	xx	xx	xx

All applicable statistical tests will be 2-sided and will be performed using a 5% significance level. 95% (2-sided) confidence intervals (CIs) will be presented. All analyses are seeking to show a difference, rather than equivalence or non-inferiority.

Where there is missing data for an outcome variable, in the first instance, those records will be removed from any formal statistical analysis relating to that outcome variable, unless otherwise specified. In tabulations, numbers of missing observations will be provided, but percentages will not include them.

The main statistical analyses for primary and secondary outcomes will be adjusted for centre and smoking status (from randomisation stratification) and baseline values of 'Previous treatment with 6MP' and 'Previous treatment with Azathioprine' following note from DMC in January 2013. Results of unadjusted statistical analyses will also be presented.

Distributional assumptions underlying the statistical analyses will be assessed by visual inspection of residual plots. Normality will be examined by normal probability plots. If the distributional assumptions for the parametric approach are not satisfied, further data transformation (to alleviate substantial skewness (i.e. normalizing) or to stabilise the variance), or other suitable methods will be considered. This will be documented in the statistical results report together with the reasoning supporting the action taken, if applicable.

All analyses and data manipulations will be carried out using SAS [1].

#### 6 List of analyses

#### 6.1 Recruitment and retention

The date of first and last patient randomised, the number of patients randomised, and the number of centres that recruited patients, will be reported.

A CONSORT flow chart will be provided by the TOPPIC Trial Manager. This will show the number and percentage of patients considered for randomisation, randomised, dosed, completed and discontinued by treatment and overall. Reasons for noninclusion in the study (prior to randomisation) will be categorised, as in the data monitoring committee (DMC) reports. The number of patients discontinued early from the study will be summarised by reason for withdrawal and treatment.

#### 6.2 Baseline Balance

No formal statistical testing will be performed. The following will be presented and summarised by allocated treatment:

- Consent obtained
- Variables from randomisation stratification: Centre, Smoking status. Smokers will be defined as those smoking >1 cigarette/day
- Other data recorded at pre-assessment and randomisation visits:

#### Pre-assessment

Gender Previous treatment with: 6MP/Azathioprine/Other corticosteroids Infliximab or Methotrexate No immunosuppressants Crohn's disease location & type Previous surgery TPMT Age at randomisation Age at diagnosis Duration of Crohn's disease

Randomisation/Visit 2

Weight, Height Faecal calprotectin Neutrophil count CDAI score IBDQ/EQ-5D/SF-36

#### 6.3 Adherence with trial protocol and allocated treatment

No formal statistical testing will be performed. The following will be presented:

- Number and percentage of patients who were ineligible for inclusion in trial (if any it should not have been possible to randomise such patients).
- Numbers of patients who were randomised but never treated.
- Numbers of patients who took trial medication for the full 3 years, and those who stopped early.

For those who stopped early, they will be categorised as:

Primary outcome-related event Other adverse event Blood test result Other reasons

Time to stopping medication will be presented as a Kaplan-Meier plot, split by allocated treatment.

 Prescribed dose will be summarised. Dose at final visit compared with dose at first visit will be summarised as:

> Dose increased Dose stayed the same Dose decreased Trial medication stopped early

- A summary of patients attending and withdrawing at each visit will be presented, together with reasons for withdrawal.
- A listing of patients where the blind was broken early will be presented, including details of allocation, timing and reason for breaking blind, and outcome.

#### 6.4 Concomitant Medication

Number and percentage of patients will be presented by medication, treatment and overall, in the categories used in the database. These will be split into prohibited medications, and non-prohibited medications.

For non-prohibited meds, these will be split into those used as rescue therapy, and those used for other reasons. For prohibited meds, the number of patients who take each medication type (5 ASAs, corticosteroids, anti-tumour necrosis factor, azathioprine, methotrexate, allopurinol, antibiotics for Crohn's disease, oral non-steroidal anti-inflammatory drugs) will be tabulated, split by whether these are rescue meds or not.

<sup>1 Postoperative clinical recurrence of Crohn's disease (defined by a Crohn's Disease Activity Index value of greater than 150 together with a 100 point rise in the CDAI score from baseline), together with the need for anti-inflammatory rescue therapy or primary surgical intervention.

#### 6.5 Primary Outcome

The primary outcome variable is the timing of postoperative clinical recurrence of Crohn's disease.

For the purposes of the statistical analysis, the date of recognition of clinical recurrence as assessed by the CDAI score will be considered the date of primary outcome provided that anti-inflammatory rescue therapy or primary surgical intervention is initiated as part of the same clinical episode. If there is any doubt that events form part of the same clinical episode, this will be assessed by the CI who will be blinded to the treatment allocation. It is recognised that, in some cases, rescue therapy may have been initiated before the CDAI score reaches the trigger criteria.

The primary outcome will be assessed as follows:

- a. The times, split by treatment group, will be presented using a Kaplan-Meier plot. If distributional assumptions hold, this will be analysed using Cox proportional hazards regression. The effect of treatment allocation will be reported as an adjusted (as detailed in Section 5) hazard ratio with its corresponding 95% confidence interval. Unadjusted results will be presented as a secondary analysis.
- b. Length of patient follow-up will be summarised, together with a summary of the number followed for 3 years or having a recurrence.

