#### 6.6 Secondary outcome

 A secondary outcome variable of clinical recurrence of Crohn's disease (defined by a CDAI value of greater than 150 together with a 100 point rise in the CDAI score from baseline), OR the need for anti-inflammatory rescue therapy OR primary surgical intervention will be analysed in the same way as the primary outcome.

The number of patients with each element of this combined endpoint will be summarised separately. For rescue therapy, the number of patients who take each medication type (5 ASAs, corticosteroids, anti-tumour necrosis factor, azathioprine, methotrexate, allopurinol, antibiotics for Crohn's disease, oral nonsteroidal anti-inflammatory drugs) will be tabulated in the Concomitant Medication section. For surgical intervention, the number of surgical interventions per patient will be summarised. These will be classified as primary or secondary. The time to surgery will also be summarised.

a. An informal sensitivity analysis comparing patients who are 'on-drug' versus those who are 'off-drug' at the end of their time in the trial with respect to the secondary endpoint will be presented by means of a Kaplan-Meier plot. No formal statistical testing will be performed.

<sup>2 Postoperative clinical recurrence of Crohn's disease (defined by a Crohn's Disease Activity Index value of greater than 150 together with a 100 point rise in the CDAI score from baseline), together with the need for anti-inflammatory rescue therapy or primary surgical intervention.

- Endoscopic recurrence using both the Rutgeert's and CDEIS scoring system will be summarised by time and treatment group. Colonoscopy results will also be summarised.
- 3. Colonoscopy results at Visit 12 will be compared between the treatment groups using a chi-squared test. CDEIS scores at Visit 12 will be compared between the treatment groups using a t-test.
- 4. Faecal calprotectin results will be summarised by time and treatment group, both as a continuous measure and categorically. The continuous change from baseline to each time point will also be summarised.

The use of faecal calprotectin as a non-invasive marker of clinical recurrence of Crohn's disease will be examined in two ways:

- Levels will be compared descriptively between those with negative (≤ i1) or positive (≥ i2) colonoscopies at 12 and 36 months.

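### Baseline CDAI enters the primary event definition and is recorded at randomisation, yet no planned treatment comparison adjusts for it: a valid analysis that one pre-specified term could cheaply strengthen

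*SAP*

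**What the plan says.** **Event.** Clinical recurrence is "defined by a Crohn's Disease Activity Index value of greater than 150 together with a 100 point rise in the CDAI score from baseline" (SAP Section 6.6, footnote 2; the same rule is in footnote 1). The primary outcome also needs anti-inflammatory rescue therapy or primary surgery, and Section 6.5 requires these to belong to the same clinical episode.

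**Baseline measurement.** Section 6.2 lists CDAI among the Randomisation/Visit 2 data: "Neutrophil count CDAI score IBDQ/EQ-5D/SF-36". It is summarised by arm without testing.

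**Model.** Section 6.5a fixes the primary estimate: "The effect of treatment allocation will be reported as an adjusted (as detailed in Section 5) hazard ratio". In Section 5, to which it refers, the main analyses "will be adjusted for centre and smoking status (from randomisation stratification) and baseline values of 'Previous treatment with 6MP' and 'Previous treatment with Azathioprine". Section 5 says that this follows a DMC note of January 2013. The protocol text reproduced in Section 4 agrees: "The primary analysis will include terms for the treatment, the variables on which the randomisation was stratified and adjusted for baseline values of previous treatment". The two drugs it names there are the same two, and baseline CDAI is not mentioned.

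**Other Cox analyses of treatment.** "Unadjusted results will be presented as a secondary analysis". The subgroups in Section 6.8 do not include baseline CDAI. The prediction model in Section 6.9 is a separate exploratory report and does not re-estimate the treatment effect.

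**The concern.** The covariate list omits a baseline value that is written into the endpoint. Two patients with the same later CDAI can be classified differently because they started at different values. That makes baseline CDAI a natural candidate covariate, at the cost of one degree of freedom and no new data.

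Three things are at stake, all modest:

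- In a Cox model, leaving out a prognostic covariate moves the treatment hazard ratio a little towards 1.
- Some power is lost.
- If the Section 6.2 table shows baseline CDAI unevenly spread between arms, no adjusted analysis is on file. Any adjustment would then be chosen after seeing the data.

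**Working it through.** **1. Inputs.** From the SAP: target of 234 patients, 1:1 (Section 3); two-sided 5% (Section 5); 3 years (Section 6.5b); event rule and covariate list as above. I take the Visit 2 CDAI as the baseline in the event rule. The SAP gives no power, effect size, event rate, drop-out or CDAI distribution, so 234 cannot be reproduced and everything in steps 4 to 6 rests on assumptions.

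**2. Threshold.** Required CDAI = max(150, baseline + 100).

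| Baseline | 0 | 25 | 50 | 75 | 100 | 140 |
|---|---|---|---|---|---|---|
| CDAI to reach | 150 | 150 | 150 | 175 | 200 | 240 |

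Baseline moves the threshold only above 50.

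**3. Direction.** Suppose later CDAI rises on average by r points per point of baseline. The distance left to the threshold then changes by −r per point below 50 and by 1 − r per point above 50. With r = 0.2 the slopes are −0.2 and +0.8; with r = 0.8 they are −0.8 and +0.2. A higher baseline brings the event closer below 50 and moves it further off above 50. The net sign depends on where patients start and on how persistent CDAI is. A simulation of the CDAI rule alone (13 assessments, about 43% events) gave hazard ratios per SD of baseline from 0.51 (mean baseline about 92, r = 0.2) through 0.99 (mean about 48, r = 0.5) to 1.29 (mean about 32, r = 0.8).

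**4. Effect of leaving out a prognostic covariate.** Cox fits with and without one standardised baseline covariate; 117 per arm, 3 years, true hazard ratio 0.5, 2,000 trials per row.

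| Placebo hazard per year | Covariate log-HR per SD | Power without / with | Mean HR without / with |
|---|---|---|---|
| 0.12 | 0 | 70.3% / 70.2% | 0.491 / 0.491 |
| 0.12 | 0.2 | 69.5% / 70.0% | 0.498 / 0.495 |
| 0.12 | 0.4 | 71.4% / 73.3% | 0.501 / 0.494 |
| 0.12 | 0.7 | 69.6% / 76.6% | 0.519 / 0.493 |
| 0.06 | 0.2 | 43.6% / 44.3% | 0.484 / 0.482 |
| 0.06 | 0.4 | 45.4% / 46.2% | 0.486 / 0.481 |
| 0.06 | 0.7 | 46.8% / 50.0% | 0.505 / 0.490 |

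The gain is 0.5 to 1.9 points at 0.2 to 0.4 per SD, and 3.2 to 7.0 points at 0.7. The standard error of the log hazard ratio does not fall (0.281 against 0.282 at 0.4; 0.268 against 0.269 at 0.7, both at hazard 0.12). With a true hazard ratio of 1, rejection was 3.8% to 5.3% without the covariate and 4.1% to 5.2% with it.

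**5. CDAI-path simulation.** Simulated CDAI paths under the CDAI rule (234 patients, 13 assessments, baseline mean 70 to 110, SD 50 to 80, r from 0.2 to 0.8, hazard ratio 0.50 to 0.55, 1,500 trials per scenario) gave a power change of −0.4 to +3.1 points from adding linear baseline CDAI. A change of slope at 50 added nothing material. Steps 4 and 5 together give about 0 to 3 points for weak to moderate prognosis.

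**6. Chance imbalance.** SD of the between-arm difference = √(2/117) = 0.131 baseline SDs; 95% range ±1.96 × 0.131 = ±0.256. The hazard ratio then shifts by at most exp(0.256 × log-HR per SD): 1.05, 1.11 and 1.20 for 0.2, 0.4 and 0.7.

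**The case against.** The strongest reply is that nothing here is wrong. The covariate set is explicit, agrees with the protocol text in Section 4, has a stated origin, and gives a valid test. Omitting an optional covariate is not a contradiction. That stands, and it is why the point is only a suggested improvement.

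Three stronger readings are tempting, and the documents do not support them:

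- **That baseline sets every patient's threshold.** At 50 or below it is 150 whatever the baseline. The event also needs rescue therapy or surgery, and Section 6.5 accepts that rescue may start before CDAI reaches the trigger. None of the simulations modelled that requirement or the listed covariates.
- **That the omission leaves removable noise, or biases the hazard ratio through imbalance.** The Cox standard error did not fall on adjustment. Chance imbalance is covered by randomisation and the confidence interval, so leaving it unadjusted costs efficiency only.
- **That baseline CDAI must be strongly prognostic because it is in the rule.** Step 3 shows that the net association can be protective, nil or harmful.

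It can also be said that the gain may be nil. True, but so is the penalty: with no prognostic value, power was 70.3% without the term and 70.2% with it.

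**Conclusion.** The point holds as a low-cost improvement. The SAP fixes an endpoint whose CDAI threshold depends on baseline above 50, collects that baseline, and plans no treatment comparison adjusted for it. The planned primary analysis remains valid.

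If baseline CDAI is weakly to moderately prognostic, the loss is about 0 to 3 points of power with slight attenuation. Larger losses (3 to 7 points) need a log hazard ratio of about 0.7 per SD, which nothing in the SAP establishes. All sizes depend on assumed event rates, effect and CDAI behaviour.

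The firmest benefit is procedural: an adjusted result named in advance cannot be called post hoc if the arms differ at baseline.

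A reader might extend this fully to the first secondary outcome, which uses the same CDAI rule. That endpoint also counts rescue therapy or surgery on its own, so baseline CDAI matters less there. It was not simulated, and the case is weaker.

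**What to change.** Either of two edits, made before unblinding:

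1. Add baseline CDAI (Visit 2) as one continuous term to the Section 5 list for the primary Cox model, with a change of slope at 50 if wanted. Make the matching edit to the protocol model in Section 4, and keep the currently listed model as a supportive analysis.
2. If the protocol's list is to stay unchanged, add one line to 6.5a naming the CDAI-adjusted model as a pre-specified sensitivity analysis.

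In either case, state how a missing baseline CDAI is handled, so that no randomised patient silently leaves the model. Adjustment of the secondary composite can be optional.

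The cost is one degree of freedom (two with the slope change) and a short SAP edit, plus a protocol edit under the first option. The data are already collected. The downside is changing a settled covariate list for a gain that is modest and may be nil; the second option avoids that.
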